Following study completion treatment status and patient reported outcomes determined through retrospective chart review based on EHR data.

Data and Specimen Banking*

PROTOCOL TITLE: EHR Embedded Comparative Effectiveness Studies

Study data are derived from responses to the surveys. Patient level data files will be maintained until a final report is released. Full name, email and phone number will be entered into RedCap database and will only be stored with the study team.

Sharing of Results with Subjects*

Summary results from the demonstrations will be available as a published final report from the funding agency (PCORI), and in scientific publications. Information on the location and timing of summary results will be communicated to participating patients during the consent process.

Study Timelines*

The anticipated start date for enrollment into the study is September 1, 2020. Approximately three months is expected for enrollment. Patients will be contacted 1-6 months following enrollment for follow-up surveys. The estimated date for completion of the last enrollment is December 1, 2020, with the last follow-up survey completed by March 1, 2021. The primary data analyses will be executed on a blinded basis as survey data are accrued, and summarized by the end of March.

PROTOCOL TITLE: EHR Embedded Comparative Effectiveness Studies

Inclusion and Exclusion Criteria*

CPS

Inclusion Criteria: Adults (>18) able to consent, with sufficient fluency in English; indications for discectomy; able to restrict activities or to resume activities as tolerated.

Exclusion Criteria: Pregnant women; Prisoners; Children (<18).

WWC

Inclusion Criteria: Adults (>18) able to consent, with sufficient fluency in English; initial RD and HC visits are part of routine care as recommended by the provider; willing to be randomized.

Exclusion Criteria: Pregnant women; Prisoners; Children (<18).

Vulnerable Populations*

N/A

Local Number of Subjects

WWC: 60 patients total, 30 in each treatment arm.

CPS: 60 patients total, 30 in each treatment arm.

Recruitment Methods

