The consent process may take place in person at the WWC, or over the phone, or via videoconference. The participant will be asked to provide their preferred email during this conversation or address if they do not have email or internet. Both phone and videoconference process will be standardized and involve using the script provided for the WWC for the initial RD and HC visit order. The information sheet will be emailed to the participant via a RedCap link or mailed if unable to be emailed.

In CPS for the post-discectomy Activity Restriction/Activity as Tolerated, following the SOP: Informed Consent Process for Research (HRP-090).

Process to Document Consent in Writing

Given the minimal risk, a waiver of documentation of written consent is requested for this protocol. Note that all data are collected via anonymous survey, and no HIPPA data are collected.

Note that both WWC and the CPS have reviewed and approved this protocol. Consent scripts are attached as well as a detailed information sheet for each comparison, covering all required consent elements.

A waiver of HIPPA authorization is requested for the retrospective use of EHR data and chart reviews for patients who are no longer participating in the study. The data are requested to assess the feasibility of our embedded systems and processes, and, as in other retrospective EHR chart reviews, it is not practicable to obtain consent. The privacy risks are mitigated by the use of deidentified analytic data sets, which are securely stored. The files linking the study IDs to patient records will be destroyed at the conclusion of the study. PHI will not be reused or disclosed following the conclusion of the study.

Setting

The study will be conducted in the Department of Medicine D-H Weight & Wellness Center Clinic and in the Department of Orthopedic Surgery Center for Pain and Spine. All interventions are standard of care and will be performed at these sites. The DH Research Ethics Committee serves as an advisory board and includes community representation.

Resources Available

There are approximately 150 patients per year/75 per 6 months who undergo lumbar discectomy at DHMC, of whom we plan to enter 30 to each of the two arms for activity restriction following discectomy.

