Current WWC volume is estimated at approximately 600 patients per year (300 during the randomization period of 6 months, with capacity for up to 30. We plan to enroll 30 in the RD then HC initial visit, 30 for HC then RD initial visit;

PROTOCOL TITLE: EHR Embedded Comparative Effectiveness Studies

The participating clinic investigators are all part of the research team and have been meeting multiple times per month since the beginning of the study to plan the procedures and informatics. The first two weeks of the accrual period will be used to conduct the testing and provide final guidance for the clinical staff.

The facilities used for conducting the research include the clinic sites, the Department of Biomedical Data Science, Divisions of Biostatistics and Biomedical Data Sciences, The Dartmouth Institute, and the D-H Analytics Institute. The project supports approximately 40% FTE for the Investigators and Co-Investigators and 120% FTE for staff in supporting roles as research assistants and programmers. Informed consent will be performed by clinic investigators and clinic assistants, most of whom are regular participants in team meetings. Scripts and training will be reviewed prior to initiation of the demonstration projects.

Multi-Site Research*

One of our Co-Investigators, [name], has moved to the University of North Carolina (UNC). To maintain his involvement in this and other of his studies at Geisel and at Dartmouth-Hitchcock, we have changed the designation of this trial to a multi-site trial, including UNC. The appropriate materials for this change were uploaded in MOD00011236.

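### The dated three-month enrolment window is expected to hold about 37 discectomy patients against a CPS target of 60, and nothing reconciles it with the six-month periods in Resources Available

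*Combined protocol and SAP*

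**What the plan says.** Study Timelines gives one enrolment calendar for the whole study. It says "The anticipated start date for enrollment into the study is September 1, 2020" and "Approximately three months is expected for enrollment". It then says "The estimated date for completion of the last enrollment is December 1, 2020, with the last follow-up survey completed by March 1, 2021", with the analyses "summarized by the end of March". CPS has no window of its own. Data Management and Confidentiality also places completion of the full study around March 2021.

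Local Number of Subjects states the target: "CPS: 60 patients total, 30 in each treatment arm". The Study Summary gives the same size.

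Resources Available states the supply: "There are approximately 150 patients per year/75 per 6 months who undergo lumbar discectomy at DHMC". The same sentence then draws the CPS target from that volume: "of whom we plan to enter 30 to each of the two arms for activity restriction following discectomy". The next paragraph gives the WWC volume as "300 during the randomization period of 6 months". It also says that the first two weeks of accrual are for testing and final guidance to clinic staff.

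The precision table, printed under Data Management and Confidentiality, gives 90% confidence interval half-widths for rates in each arm at N = 30: 13%, 15% and 16% for rates of 80%, 70% and 60%.

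**The concern.** The target and the supply figure look compatible when read against six months. Read against the dated window, which is half as long, they are not: the stated volume falls well short of 60 before anyone is found ineligible or declines.

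Two things depend on this. The first is precision. The table assumes 30 per arm, and if enrolment stopped on the stated date the CPS arms would be smaller and their intervals wider than shown. The second is the calendar. If 30 per arm is kept, last enrolment moves, and the dates that follow it move too. The protocol does not say which gives way. Feasibility is the study's primary objective, so the enrolment plan should agree with the plan's own volume figure.

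**Working it through.** **Inputs.** Volume about 150 discectomies a year, two testing weeks and the six-month period (Resources Available). Window 1 September to 1 December 2020, which is 91 days (Study Timelines). Target 60, 30 per arm (Local Number of Subjects). Half-widths 13/15/16% at N = 30 (precision table).

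**1. The plan's own figures reproduce.**
- Six-month volume: 150 × 6/12 = 75, as stated.
- Precision table: half the width of the exact (Clopper-Pearson) 90% interval at n = 30 is 13.3/14.9/15.8% for rates of 80/70/60%, which rounds to the stated 13/15/16%. The table is correct for its N.

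**2. Expected supply in the dated window.**
- By months: 150 × 3/12 = 37.5. By days: 150 × 91/365 = 37.4.
- Share of target: 37.5/60 = 62.5%, an expected shortfall of 60 − 37.5 = 22.5.
- If nobody enrols in the testing weeks (an assumption; the text does not say): 150 × (91 − 14)/365 = 31.6, about 32.

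**3. Could chance close the gap?** With a Poisson count of mean 37.4 (an assumption), the central 95% range is 26 to 50 and P(60 or more) is about 0.0004, with every patient enrolling. For the window to hold 60 on average, annual volume would have to be 60 × 12/3 = 240, which is 1.6 times the stated 150.

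**4. Time to 60 at the average rate.** 150/12 = 12.5 a month, and 60/12.5 = 4.8 months. That is 146 days from 1 September 2020, about 25 January 2021. If 80% enrol (an assumption), 60/(12.5 × 0.8) = 6.0 months.

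**5. Six months.**
- 60/75 = 80% of the expected patients would have to be eligible and enrol.
- If the testing weeks enrol no one: 75 − 150 × 14/365 = 69.2, and 60/69.2 = 87%.

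**6. Per-arm precision at the expected size** (same exact method, evaluated at exactly 80/70/60%).

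| n per arm | Basis | Half-width at 80/70/60% |
|---|---|---|
| 30 | as planned | 13.3/14.9/15.8% |
| 19 | 37.5/2 = 18.75, rounded up | 16.9/18.9/20.0% |
| 15 | 37.5 × 0.8/2, if 80% enrol (assumption) | 19.2/21.3/22.5% |

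The last entry is 22.48% before rounding, so 22% in whole percents.

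**7. WWC for comparison.** 600 × 3/12 = 150 patients in three months against a target of 60. On volume, WWC is not short.

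**The case against.** The strongest reply is that the timeline is a forecast. Study Timelines words its dates as anticipated, approximate or estimated, and no text closes enrolment on 1 December if 60 has not been reached. A slip in dates alone would leave the design, the analysis and the precision table as they are. This stands as a reason to rate the point lower. It does not remove it, because the gap is a factor of 1.6 and nothing in the text foresees an extension.

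Four further limits apply.

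- **37 is an average, not a ceiling.** A reader might infer that an arm cannot exceed 19 or that 60 cannot come before 25 January 2021. The volume is approximate, and under the Poisson assumption more than 38 patients would appear about 42% of the time. Also, CPS patients are identified by the surgeon's order, while the 150 counts operations. What stands is that 60 is very unlikely.
- **The six-month CPS window is inferred.** The phrase about a six-month randomization period is in the WWC sentence; for CPS there is only a volume quoted per six months. The shortfall does not depend on this inference, since the dates and the annual volume are enough to show it.
- **The consequence is descriptive.** The hypotheses are stated by clinic. If CPS rates are pooled over arms, the exact 90% half-widths are about 12/13/14% at n = 37 against 9/10/11% at n = 60. The 17/19/20% figures apply to the per-arm display that the protocol chose to tabulate.
- **Multi-site status.** The added university site is explained as keeping a co-investigator involved, and no added patients are described. It does not supply the difference.

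**Conclusion.** The inconsistency holds. On the stated volume, the dated window is expected to yield about 37 discectomy patients (about 32 if the testing weeks enrol no one) against 60. Either the dates or the CPS size and per-arm precision must give way. If the dates are kept, the per-arm half-widths widen by about 4 points at 19 per arm and by about 6 points at 15 per arm.

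The result rests on the stated approximate volume, even accrual over the year and, for the probability, a Poisson count. The 80% uptake and the empty testing weeks are assumptions, used only for the figures marked as such.

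Three stronger readings are not supported. The precision table is not wrong, since it is correct for N = 30. The shortfall does not bias the results or weaken a between-arm comparison, since the documents plan no such test. And the need for 80% uptake over six months does not contradict the plan: it is in line with the hypothesis of more than 80% participation (whose denominator is not defined), though it leaves little or no room for ineligible patients.

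This is a planning inconsistency of modest severity that affects stated size, precision and dates, and it is worth correcting because the correction is cheap.

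**What to change.** State one enrolment window for CPS and make the dependent text agree with it. Either option changes wording, dates and figures only.

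**Option 1: adopt the six-month period.** Last enrolment moves by about three months, to about 1 March 2021. With surveys sent 1 to 6 months after enrolment, the last survey falls no earlier than about 1 April 2021. The analysis date in Study Timelines and the completion date in Data Management and Confidentiality move after it. State that 60 needs about 80% of the expected 75 patients, or about 87% of about 69 if the testing weeks enrol no one, and say whether patients are enrolled in those weeks. The cost is the later calendar, with some remaining risk of falling short of 60.

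**Option 2: keep the three-month dates.** Restate the expected CPS size as about 37 or fewer, and give the CPS per-arm 90% half-widths at that size: about 17/19/20% at 19 per arm, or about 19/21/22% at 15 per arm if 80% enrol (an assumption). The cost is a less favourable precision statement. The WWC figures need no change on this account.

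One matter should be kept apart. The Study Summary gives CPS patients six months of follow-up. If the last survey must close that follow-up, a 1 December 2020 enrolment already runs to 1 June 2021, past the 1 March 2021 date for the last survey. That conflict exists under either window, needs its own reconciliation, and its delay should not be counted as a cost of this fix.
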